2. AIM/ OBJECTIVES

To compare the clinical outcome in the form of safety, efficacy and cost effectiveness between Holmium laser enucleation of the prostate versus bipolar transurethral enucleation of the prostate

3. METHODOLOGY:

Patients and Methods/ Subjects and Methods/ Material and Methods

Type of Study: prospective randomized clinical trial

Study Setting: Operation ward - Ain Shams University hospitals.

Study Period: 4/2018 till we finish the follow up period

Study Population: Egyptian male patients attending Ain Shams University hospitals Urology clinic

Sample size: It was dose using STATA program, setting alpha error at 0.05 and power at 90% based on results from previous study (Enikeev et.al,2018) that showed a mean catheter removal time in HoLEP group was 1.3 -/+0.6 while in Transurethral electrocautery enucleation group was 3.8 -/+1.7 (9), based on that, the needed sample is 50 cases per group taking in account 20% drop out rate.

Group A: 50 Patients will undergo prostatic resection using HoLEP

Group B: 50 Patients will undergo BPEP

Procedures: each procedure will be done by 2 expert surgeons who performed over 50 cases of enucleation with each energy source. In group 1, the HoLEP procedure will be done under either

general or spinal anesthesia, using a Holmium laser device (cyber Ho 100-watt, Quanta device, Milano, Italy) with a 50-watt power, 2.5 joules and 25 MHz frequency. A 550 nm flexible laser fiber. In group 2, the BPEP procedure will be done by a Karl Storz device, using a bipolar resection loop or button loop according to the availability and surgeon's preference, tissue morcellator with reusable blades (Ricjard Wolf Inc.) will be used to morcellate the prostatic adenoma.

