The enucleation technique is nearly similar in both groups regardless of the energy source used, a 26 Fr continuous flow resectoscope (Karl Storz, Germany) with saline irrigation. The procedure will start by incision along the deepest prostatic groove using a bilobed technique where each lobe will be enucleated separately or a trilobed technique to separate a huge median lobe first then to continue as bilobed technique, the incision continues till verumontanum, then we will perform a circumferential marking proximal to the external urethral sphincter for demarcation, lateral incision will be done till the prostatic capsule and start enucleation using a mechanical force of the resectoscope with assisted energy source either Holmium laser or bipolar electrocautery, and then we will proceed anterolateral around the prostatic adenoma, aiming for early apical separation to avoid traction of the external sphincter with mucosal strip to be left intact more proximal to avoid dissemination of energy to the sphincter, anterior commissurotomy to be done to separate each lobe separately the procedure mimic figure enucleation in open surgery by using the resectoscope assisted energy source and then to proceed anteriorly till the bladder neck and then we complete the enucleation from anterior to lateral and move downward to finally separate the adenoma from posteriorly into the bladder, in this way we avoided the sub-trigonal injury or ureteric injury, then we perform the other lobe in the same way, after separation of each lobe we check the ureteric orifices and adequate hemostasis was done, finally morcellator will be used to cut down prostatic adenoma into small chips to be removed.

Inclusion criteria: Men who are fit for surgery and need a surgical resection of the prostate larger than 80 ml including:

1. Bothersome LUTS with an IPSS score over 19
2. Refractory hematuria
3. Upper urinary tract affection
4. Recurrent UTI secondary to prostatic enlargement
5. Maximum uroflow rate (Qmax) below 10 ml/sec.

6. bladder diverticula
7. Urinary retention whether recurrent acute attacks with failure of medical treatment or chronic retention.

Exclusion criteria: Patients with:

1. Neurogenic bladder
2. Previous prostate or urethral surgery
3. Associated urethral stricture
4. Prostate cancer diagnosed by TRUS biopsy
5. Bladder stones,

Ethical Considerations: Approval will be obtained from the ethical committee at Ain shams University before starting the research.

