Study Procedures: The patients will undergo the following:

Preoperative:

1) History:

Including medical history, surgical history, drug history, International Prostate Symptom Score (IPSS) and quality of life score (QoL).

2) Clinical Examination:

Including abdominal, pelvic and digital rectal examination (DRE).

3) Laboratory investigations:

As Haemoglobin level, serum creatinine, urea, sodium, potassium and prostate specific antigen (PSA).

4) Radiological investigations:

As pelvi-abdominal ultrasound to assess prostate volume and postvoiding residual urinary volume (PVR).

5) Maximum Flow Rate (Qmax).

Intraoperative: Vital data monitoring, operative time and the need for blood transfusion

Postoperative Follow-up Protocol:

Patients will be evaluated immediately postoperative with vital signs (Blood pressure, Heart rate), abdominal examination, degree of haematuria, haemoglobin level drop and Sodium level changes.

Patients will be re-evaluated at 6 and 12 months postoperatively with the IPSS, QoL, Pelvic U/S (to assess prostate volume and post voiding residual urinary volume (PVR)) ,

Maximum Flow Rate (Qmax) and Total PSA .

Data collection and outcome measures:

Primary outcomes:

1. Catheter removal time

Secondary Outcomes:

1. Operative time, enucleation time
2. Intraoperative need of blood transfusion and hemoglobin drop
3. Conversion to other type of surgeries
4. Post-operative drop in hemoglobin level
5. Duration of hospital stay
6. Postoperative complication: urinary tract infection, stress incontinence, hematuria, urine retention
7. Post voiding residual urine, Qmax, PSA, Prostate volume, QoL and IPSS 1 and 12 months postoperative
8. Delayed complication up to 12 months postoperative including urethral stricture, urinary retention, incontinence or bladder neck contracture.
9. Cost effectiveness of each procedure.

Statistical Analysis: The data will be collected, processed and statistically analyzed. Description of the quantitative variable will be done as mean and standard deviation and student t-test will be used to compare the two groups in parametric data while the qualitative data will be shown as frequency and compared using Chi square test. The results will be considered significant with P-value less 0.05 and high significant if less than 0.01, results with P-value ≥ 0.05 will be considered non-significant. Analysis of the data will be done using IBM SPSS software (Statistical program for social science version 21).

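### Operative and enucleation time are compared without adjustment for prostate volume, which is measured before surgery and has no upper limit, so precision is lost.

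*Combined protocol and SAP*

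**What the plan says.** All of this is in section 3, Methodology, of the combined protocol and SAP.

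- **Outcome.** Secondary Outcomes item 1 reads "Operative time, enucleation time". Neither time has a start point, a stop point or a unit.
- **Intraoperative record.** Under Study Procedures the list reads "Intraoperative: Vital data monitoring, operative time and the need for blood transfusion". Operative time is the only duration in it. Morcellation time and retrieved tissue weight appear nowhere in the document.
- **Eligibility.** The population is "Men who are fit for surgery and need a surgical resection of the prostate larger than 80 ml". Neither the inclusion nor the exclusion criteria set an upper limit, and no stratification by volume is described.
- **Baseline volume.** The preoperative work-up includes imaging: "As pelvi-abdominal ultrasound to assess prostate volume and postvoiding residual urinary volume (PVR".
- **Analysis.** "student t-test will be used to compare the two groups in parametric data". No covariate, transformation or alternative for skewed data is given.
- **Morcellation.** The technique described for both groups ends with "finally morcellator will be used to cut down prostatic adenoma into small chips to be removed". The equipment paragraph mentions the device only in the sentence on group 2: "tissue morcellator with reusable blades (Ricjard Wolf Inc.) will be used to morcellate the prostatic adenoma".

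**The concern.** Time to enucleate a gland is likely to depend on how large the gland is. With a floor of 80 ml and no ceiling, part of the spread in both times will come from gland size and not from the energy source. A t-test on unadjusted times leaves that spread in the error term, although the variable that would explain it is already measured in everyone. A real difference between holmium laser and bipolar enucleation is then harder to detect, and its confidence interval is wider than it need be.

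Two lesser points go with this. Enucleation time is a named outcome, but it has no definition and no listed recording step. Operative time, if it runs to the end of the procedure, adds morcellation, which does not use the energy source under comparison, to the step where the arms differ.

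**Working it through.** **The plan's own figure.** There is none for operative or enucleation time. The 50 per group was derived for catheter removal time, so it is taken here as given and nothing guarantees its power for the time outcomes.

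**Inputs.** From the plan: 50 per arm, or 40 after the stated 20% dropout; alpha 0.05, taken as two-sided. Assumed, because the documents are silent: correlation r between volume and time of 0.3, 0.5 or 0.7, and a true difference of 0.5 SD of time.

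**1. Interval width.** Adjusting for a baseline covariate multiplies the residual SD by √(1 − r²).
- r = 0.3: √0.91 = 0.954, about 5% narrower
- r = 0.5: √0.75 = 0.866, 13% narrower
- r = 0.7: √0.51 = 0.714, 29% narrower

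**2. Power.** Power = Φ(0.5 / [√(1 − r²) × √(2/n)] − 1.96). At n = 50, √(2/50) = 0.2, so the unadjusted test has Φ(2.5 − 1.96) = 70.5%.

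| Per arm | Unadjusted | r = 0.3 | r = 0.5 | r = 0.7 |
|---|---|---|---|---|
| 50 | 70.5% | 74.6% | 82.3% | 93.8% |
| 40 | 60.9% | 65.0% | 73.3% | 87.9% |

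Leaving volume out costs about 4 to 23 points of power at 50 per arm and 4 to 27 at 40.

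**3. Chance imbalance.** At 50 per arm the 95% limit of the difference in mean volume is 1.96 × 0.2 = 0.392 SD. This shifts the time difference by r × 0.392 = 0.12, 0.20 or 0.27 SD. In a trial that happens to have this imbalance, the unadjusted test rejects a true null in 7.9%, 12.9% or 20.5% of cases. With a smaller imbalance of 0.2 SD the rates are 5.0%, 4.8% and 3.9%. Over all randomisations the rate is 5%.

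To put this in minutes, assume a volume SD of 40 ml and 0.5 min per ml. The limit is then 1.96 × 40 × 0.2 = 15.7 ml, or 7.8 min. The same inputs imply a time SD of 0.5 × 40 / r, which is 40 min at r = 0.5 and 28.6 min at r = 0.7. The unadjusted 95% half-widths are 1.96 × 0.2 × SD = 15.7 and 11.2 min. The 7.8 min is therefore r times an uncertainty that the t-test already reports.

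**4. Morcellation within operative time.** Suppose the device affects only enucleation, by 0.5 of its SD, and independent morcellation time has an SD q times as large. The SD of the sum grows by √(1 + q²). At 50 per arm, power falls from 70.5% to 60.9% for q = 0.5 and to 42.4% for q = 1. This concerns operative time only.

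**5. Covariate or ratio.** Simulation used 50 per arm, a 0.5 SD effect, volume equal to 80 ml plus a skewed excess with SD 40 ml, r from 0.3 to 0.7, and 0 to 60 min of time that does not depend on volume. Power was about 70% for raw time, 67% to 92% for minutes per ml, and 73% to 93% for analysis of covariance. The ratio does well only when time is close to proportional to volume.

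**The case against.** Several stronger readings are tempting, and the documents do not support them.

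- **That only total operative time is recorded.** Enucleation time is named under Data collection and outcome measures. The intraoperative list is plainly not exhaustive: Study Procedures also omits catheter removal time, which is the primary outcome, as well as hospital stay and cost. What stands is a mismatch between two lists and a missing definition.
- **That gland size biases the comparison.** The trial is randomised, so volume differs between arms only by chance, and the t-test's standard error already contains that variation. What stands is the loss of precision and the distortion in an individual trial with a large imbalance.
- **That the measure cannot isolate the energy-dependent step.** Enucleation time in its ordinary meaning leaves out morcellation. Operative time is also a legitimate outcome in its own right and may bear on cost effectiveness (item 9).
- **That conversions make an arm look faster.** Conversion might follow a short attempt or a prolonged one, and the plan does not say. Only the absence of a timing rule stands. Adenoma left behind would be partly visible in postoperative prostate volume and PSA (item 7).
- **That the absence of a size ceiling is a defect.** Glands above 80 ml are the stated target population. The open range is only a reason to use the measured volume.

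**Conclusion.** The point holds as a matter of efficiency and definition. Both times are compared by a test that ignores a baseline variable already measured in every patient. For r between 0.3 and 0.7, adjustment would narrow the interval by about 5% to 29% and raise power for a 0.5 SD effect at 50 per arm from 70.5% to between 74.6% and 93.8%. These figures rest on the assumed correlation and effect size and on a roughly linear relation between volume and time; at a correlation near zero the gain disappears. Type I error is not inflated overall. Since these are secondary outcomes, this is a worthwhile improvement and does not threaten the trial's main conclusion.

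**What to change.** 1. Analyse operative time and enucleation time by analysis of covariance on preoperative ultrasound volume, in all randomised patients, using log time if the distribution is skewed. Still list raw times by arm. A covariate is preferable to minutes per ml, which assumes proportionality.
2. Define start and stop points for both times, and add enucleation time to the intraoperative record.
3. Record morcellation time and retrieved tissue weight. Report enucleation efficiency (g per minute) as a supplementary descriptive measure only, because retrieved weight is measured after treatment.
4. Keep converted cases in the operative-time comparison and list them separately as well. Excluding them would be a post-randomisation exclusion on something the trial itself compares (item 3). State in advance how their times are counted.
5. Reconcile the equipment paragraph with the technique description on whether the morcellator is used in both groups.

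The adjustment needs no new data. The rest costs a few clock times and one weighing per case, plus a little more analysis work. Timings and weights cannot be recovered reliably after surgery, so the recording has to be specified beforehand.

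### The 12-month efficacy comparison (item 7) ignores re-treatment and catheter status, and these events are not collected after surgery, so it can favour an arm with more failures

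*Combined protocol and SAP*

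**What the plan says.** All of this stands in Section 3 (Methodology) of the combined protocol and SAP.

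- Secondary Outcomes, item 7, gives the efficacy measures: "Post voiding residual urine, Qmax, PSA, Prostate volume, QoL and IPSS 1 and 12 months postoperative". No condition is attached about catheter status or treatment since the operation.
- The postoperative follow-up paragraph gives the visits: "Patients will be re-evaluated at 6 and 12 months postoperatively with the IPSS, QoL, Pelvic U/S". It says 6 and 12 months where item 7 says 1 and 12. The two must be reconciled, but both include month 12.
- Secondary Outcomes, item 8, counts late failures as a separate outcome: "Delayed complication up to 12 months postoperative including urethral stricture, urinary retention, incontinence or bladder neck contracture". Item 6 counts early complications, retention among them.
- The Statistical Analysis paragraph says that "student t-test will be used to compare the two groups in parametric data", with a chi-square test for qualitative data. It defines no analysis set and gives no rule for missing values or for values measured after a second procedure.

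Further procedures, re-catheterisation and restarted BPH medication are not named as outcomes or as follow-up data. Drug history appears only in the preoperative list. The conversion outcome (item 3) is most naturally read as a change of technique during the index operation.

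**The concern.** Item 8 expects stricture, contracture and retention within the same 12 months over which item 7 is measured, and these events bear on whether and how item 7 can be read. A man with an indwelling catheter at the visit has no free-flow Qmax and no meaningful PVR, so he is absent from those t-tests. A man whose stricture or contracture was successfully treated in the interval brings the flow and symptom score that follow the repair, credited to the energy source that needed repairing. Both effects make an arm with more failures look better.

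The entry criteria show that these conditions matter. Men with a stricture, or with earlier surgery on the prostate or urethra, are excluded at baseline, yet a re-treated man may have either by month 12 and is analysed like any other. Men in chronic retention are eligible, so failure to void after surgery is foreseeable.

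Efficacy is a stated aim, and so is cost effectiveness (item 9). A second procedure is a cost, and no dated record of one is planned. Without dates, an analyst cannot tell later which 12-month values came after a repair.

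**Working it through.** **Is there a planned figure to reproduce?** None bears on this point. The only sample-size statement, "the needed sample is 50 cases per group taking in account 20% drop out rate", rests on catheter removal time. The documents give no failure rate and no expected Qmax, IPSS or PVR. Every rate and mean below is therefore an assumption.

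**Step 1. Which men are affected, following the plan as written.**

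| Man at 12 months | Qmax and PVR | IPSS | Counted in items 6 or 8? |
|---|---|---|---|
| Failure, no catheter, not re-treated | Poor value, correctly included | Poor value, correctly included | Yes, if stricture, retention or contracture |
| Catheter in place | No usable value; leaves the t-test | May be recorded; hard to interpret | Retention counted; catheter status not listed |
| Successfully re-treated | Post-repair value, included | Post-repair value, included | Diagnosis counted; procedure and date not listed |
| Re-treated without success | Poor value, included | Poor value, included | As above |

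Only the second and third rows distort item 7. Call the proportion of an arm in those rows f.

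**Step 2. Shift in one arm's mean.** Assume Qmax 20 ml/s after success and 5 ml/s in failure.

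- Mean with failures at their failed value: 20(1 − f) + 5f = 20 − 15f.
- Mean recorded if they are missing or repaired to the success mean: 20.
- Overstatement: 15f. For f = 0.04 this is 0.6 ml/s; for f = 0.10 it is 1.5 ml/s.

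**Step 3. Shift in the difference between arms.** This is (f in one arm − f in the other) × (success value − failure value).

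- 2% against 8% (1 and 4 of 50): Qmax 0.06 × 15 = 0.9 ml/s. IPSS, assuming 6 in success and 20 in failure: 0.06 × 14 = 0.84 points.
- Other assumed means (22 ml/s in success, 6 to 10 in failure): 2% against 6% gives 0.04 × 12 = 0.48 to 0.04 × 16 = 0.64 ml/s; 5% against 15% gives 0.10 × 12 = 1.2 to 0.10 × 16 = 1.6 ml/s.
- Equal f in both arms: 0.

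**Step 4. Against sampling error.** Take 2% against 8%, a Qmax SD of 5 to 9 ml/s among successes (assumed), failures fixed at 5 ml/s, and 40 to 50 men per arm. Each arm's variance is (1 − f)SD² + f(1 − f)15².

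- SD 5, 50 per arm: variances 24.5 + 4.41 = 28.91 and 23 + 16.56 = 39.56; standard error √(68.47/50) = 1.17.
- SD 9, 40 per arm: variances 79.38 + 4.41 = 83.79 and 74.52 + 16.56 = 91.08; standard error √(174.87/40) = 2.09.

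A true difference of 0.9 ml/s then has about 12% and 7% power. Counting every failure would seldom change the result of the t-test.

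**Step 5. Power of a failure outcome with 50 per arm** (two-sided 0.05, normal approximation; Fisher's test is more conservative):

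| Failure rates | Power | Per arm for 80% |
|---|---|---|
| 2% vs 10% | 39% | 138 |
| 5% vs 15% | 38% | 141 |
| 2% vs 6% | 17% | 376 |

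An observed 1 against 4 of 50 gives p = 0.36 by Fisher's test.

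**The case against.** The strongest reply is that failures are already visible. Items 6 and 8 record retention, stricture and contracture, the list in item 8 is open-ended, and the chi-square test compares them by arm. An excess in one arm could therefore show there even if mean Qmax does not. This stands as far as it goes. What those items lack is the procedure, its date and catheter status at the visit, and hence any link to item 7.

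A second reply is that analysing all values regardless of later treatment is a legitimate choice. That is true, but the plan does not state the choice, and the reader also needs to know how many men were re-treated. Such a rule also supplies no value for a catheterised man.

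Third, the likely shift is small against sampling error, as Step 4 shows. This also stands and limits the weight of the point.

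A reader might infer more than the documents support:

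- **That every failed operation is either lost or turned into a success.** The plan says neither. A man with a poor result, no catheter and no second procedure is measured correctly, and a second procedure need not work.
- **That the plan sets out to declare equal efficacy.** Its aim is to compare. It has no equivalence or non-inferiority claim; the remark on equal safety and efficacy in the Introduction describes earlier literature.
- **That the primary outcome is compromised.** This gap concerns secondary outcomes, not catheter removal time.

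**Conclusion.** The gap is real and worth closing. Item 7 is compared with no account of catheter status or re-treatment, and the data needed to repair this afterwards are not listed for collection. The efficacy comparison can therefore favour an arm with more failures.

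The size cannot be derived from the documents. Under the assumed 4% to 10% of masked failures and a 15 ml/s gap between success and failure, one arm's mean Qmax is overstated by 0.6 to 1.5 ml/s. This supposes that all such men are missing or restored to the success mean. With the same gap in both arms, between-arm bias arises only if the masked proportions differ. The case for change rests less on moving a p-value than on an honest account of efficacy and cost, at little expense.

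**What to change.** 1. **Collect.** At the scheduled follow-up visits, record the date and type of any further prostatic, urethral or bladder-neck procedure, any re-catheterisation, and any restarted BPH medication. This is data collection only; when to re-treat remains for the investigators.
2. **Add one secondary efficacy outcome to item 7:** the proportion at 12 months free of all three. Fix its definition before analysis, including whether a brief early re-catheterisation counts. Report it by arm with a confidence interval, and use Fisher's exact test because events will be few.
3. **Report the item 7 measures as observed,** with the number of re-treated or catheterised men in each arm beside them.
4. **Add a sensitivity analysis** that gives these men the worst rank and compares the arms with a rank test. It yields no mean and does not fit the t-test, so it belongs beside the main analysis.

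Carrying forward the last value before re-treatment is not advised. With so few visits, the last value for a man re-treated early could be his preoperative one.

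The cost is a few form fields at visits already planned and a slightly less favourable reported success rate. The new outcome has low power (17% to 39% in the cases above), so it should be read descriptively, and a non-significant result should not be taken as evidence of equal failure rates.

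### Intraoperative injury and reintervention are not named outcomes, and complications are undefined and ungraded, although safety is a stated aim

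*Combined protocol and SAP*

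**What the plan says.** The Aim/Objectives section sets out "To compare the clinical outcome in the form of safety, efficacy and cost effectiveness" between the two enucleation techniques, so safety is an explicit aim.

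The technique description in the Methodology section describes incision down to the prostatic capsule, a dissection route chosen to avoid sub-trigonal and ureteric injury, inspection of the ureteric orifices after each lobe, and morcellation at the end.

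Under Study Procedures, the intraoperative record consists of "Vital data monitoring, operative time and the need for blood transfusion". The immediate postoperative check includes the degree of haematuria, with no scale given.

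The Secondary Outcomes that bear on safety are:

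- Item 2: "Intraoperative need of blood transfusion and hemoglobin drop"
- Item 3: "Conversion to other type of surgeries"
- Item 4: postoperative haemoglobin drop
- Item 6: "Postoperative complication: urinary tract infection, stress incontinence, hematuria, urine retention"
- Item 8: "Delayed complication up to 12 months postoperative including urethral stricture, urinary retention, incontinence or bladder neck contracture"

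The Statistical Analysis section says that "the qualitative data will be shown as frequency and compared using Chi square test". It defines no composite and no total complication rate.

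**The concern.** A safety comparison can show only what the outcome list and the data collection let in. The protocol recognises certain operative injuries as hazards and has the surgeon look for one of them, but gives the finding nowhere to go. A return to theatre, for bleeding or any other reason, is not counted as such either. The complications that are listed have no definition, threshold or severity grade, so the analysis has only presence or absence to work with.

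The trial could then report similar safety for the two techniques without having prespecified organ injury or reintervention as something to compare. Reintervention also plausibly bears on cost effectiveness, which is item 9 and another stated aim.

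**Working it through.** The plan has no complication figure to reproduce. Its 50 per group is derived from catheter removal time, and this point does not rest on it. The main check is to take each type of harm and look for the outcome line that would count it.

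| Harm | Where the protocol touches on it | Outcome line |
|---|---|---|
| Ureteric orifice or sub-trigonal injury | Technique description: to be avoided; orifices checked | None, unless it leads to conversion (item 3) |
| Capsular injury | Technique description: incision reaches the capsule | None, unless conversion or bleeding follows (items 2 to 4) |
| Bladder or morcellator injury | Technique description: morcellation | None, unless conversion or bleeding follows (items 2 to 4) |
| Return to theatre or reintervention | Not mentioned | None; the cause may appear as haematuria, haemoglobin drop, stricture or a longer stay |
| Postoperative transfusion | Not mentioned | None; item 2 is intraoperative |
| Haematuria | Degree noted immediately after surgery | Item 6, without grade |
| Incontinence, retention | Follow from the procedure | Items 6 and 8, without grade |
| Stricture, bladder neck contracture | Follow from the procedure | Item 8, without grade |

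The first five rows are the gap in what is counted. The last three show that listed events are counted but not graded.

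**Within one event type.** Assume that a share *x* of each arm has any haematuria, and that 2% and 8% of the arms have a major case (clot evacuation or return to theatre) that lies within that share. If haematuria is scored present or absent, the outcome reads 50*x* in both arms. For *x* = 20% that is 10 against 10, and for *x* = 80% it is 40 against 40. The major cases are 0.02 × 50 = 1 and 0.08 × 50 = 4. The difference between the arms is invisible whatever *x* is, provided *x* is at least 8%. All these rates are assumptions that show the mechanism.

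**Whether grading would make the difference testable.** For 1/50 against 4/50:

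- Fisher: with 5 events in total, P(*k* in the first arm) = C(50,*k*) × C(50,5−*k*) / C(100,5), which is 0.0281 for *k* = 0 and 0.1529 for *k* = 1. Two-sided p = 2 × (0.0281 + 0.1529) = 0.36.
- Uncorrected chi-square: 100 × (1×46 − 49×4)² / (50 × 50 × 5 × 95) = 2,250,000 / 1,187,500 = 1.89, p = 0.17.

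Power at two-sided 0.05 and 50 per arm, for assumed true rates:

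- 2% against 8%, summing binomial probabilities over all tables with p < 0.05: about 26% by uncorrected chi-square and 9% by Fisher. With 40 evaluable (50 × 0.80, the plan's 20% dropout): 22% and 5%.
- 2% against 10%, normal approximation: (0.08 − 1.96 × 0.0475) / 0.0468 = −0.28, which gives 39%. Fisher gives 19%. With 40 evaluable: 32% and 11%.

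If an arm has no event, the one-sided 95% upper limit on its rate is 1 − 0.05^(1/50) = 5.8%, or 1 − 0.05^(1/40) = 7.2% with 40 evaluable.

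**The case against.** The strongest reply is that the plan already counts a good deal. Several readings stronger than the one given here are tempting, and the documents do not support them.

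- **That the complication lists are closed.** Item 8 is worded as including its named events, so other delayed complications can be reported under it. Only item 6 reads as a fixed list. This part of the objection stands. The open wording still cannot capture an intraoperative event, and the listed content of the 6- and 12-month visits has no complication enquiry behind it.
- **That the most serious energy-related harms are missed.** The technique text does tie one harm to energy, namely its spread to the sphincter. The consequence, incontinence, is counted in items 6 and 8. Stricture, bladder neck contracture, haemoglobin drop, intraoperative transfusion and conversion are counted too. A morcellator injury does not come from the energy source, and the documents rank no harm as most serious.
- **That minor events swamp serious ones across the safety comparison.** This would need a pooled count, and none is defined. The statistical text fits one comparison per event. The objection therefore stands across event types and fails only within one, chiefly haematuria.
- **That any pink urine will be scored as a complication.** The protocol does not say so, but it also gives no threshold that would exclude it.
- **That grading would reveal a testable difference.** It would not at this size, as the figures above show. This is a fair reason not to build a new composite of severe events and organ injury as the main safety test.

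It is also true that a serious event may leave traces in haemoglobin drop, retention or hospital stay, and that the primary outcome is untouched.

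**Conclusion.** The point holds in a limited form. Safety is a stated aim and the protocol itself identifies operative injuries as risks, but intraoperative injury and reintervention are not prespecified outcomes, and no listed complication is defined or graded. If the plan is followed as written, an injury managed without conversion or transfusion adds no safety event. A return to theatre is not counted as such, and mild and major cases of the same event count alike, even though the degree of haematuria is already noted after surgery.

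The effect on the results cannot be quantified from the documents, because they give no complication rates; every rate used above is assumed. What is lost is completeness and interpretability of the safety report. Rare harms remain untestable at 50 per arm with or without the change. This is a cheap improvement to secondary outcomes and does not affect the primary comparison.

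**What to change.** 1. Add two named secondary outcomes: intraoperative injury (capsular, bladder or morcellator, ureteric orifice), and any reintervention or return to theatre up to 12 months. Record both from the operation note and chart.
2. Reword item 6 as all postoperative complications, including the four now listed.
3. Grade each postoperative event in items 6 and 8 by Clavien-Dindo.
4. Report the number of patients with each event by arm and grade, and the number with any event of grade III or higher, as counts with confidence intervals. Present these as descriptive, not as a powered test.

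The cost is a short extra form and small cells in the graded tables. It needs no extra patients or visits.
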